5.2. Covid-19 Considerations

Due to the COVID-19 public health emergency and in alignment with the Food and Drug Administration (FDA) Guidance for Industry, Investigators, and Institutional Review Boards entitled: *FDA Guidance on Conduct of Clinical Trials of Medical Products during COVID-19 Public Health Emergency* (issued March 2020, updated 14 May 2020), henceforth referred as “*The Guidance*”, alternative measures were implemented by Jazz Pharmaceuticals (Jazz) for some subjects and/or sites participating in the study. Jazz has implemented measures, on an “as-needed” basis, to maintain trial continuity, sustain subjects’ access to study drug and ensure the continued safety of subjects and the integrity of the study data.

Where it is possible, Study JZP080-301 will be conducted in accordance with the protocol. However, for some study subjects and sites, the COVID-19 public health emergency and resulting “stay at home” orders, site closures, and travel limitations have led to difficulties in meeting protocol-specified procedures, including on-site delivery of investigational product and adhering to protocol-mandated on-site visits and laboratory/diagnostic testing for the study.

In these circumstances, alternative measures are employed and documented as protocol deviations that will be summarized within the CSR. These alternative measures are intended to remain in effect only for the duration of the public health emergency related to COVID-19, and are applied only if an on-site study visit could not occur. The measures are the delivery of study drug directly to subject’s residence or to a pharmacy near the subject’s residence and replacing on-site study visits with remote study visits, which may include:

- Adaptation of efficacy assessments
- Alternative methods for safety assessments

Guidance was provided to the sites on how to capture additional information related to COVID-19.

A listing of all subjects affected by the COVID-19 related study disruption by unique subject number identifier and by investigational site, and a description of how the individual’s participation was altered will be generated. Specifically, the listing will include, but is not limited to, the following:

- Subjects who had on-site visits converted into remote visits
- Subjects who had visits and/or assessments not performed/missing along with the reason
- Subjects who had safety and efficacy data collected out of window for the Stable-Dose or Double-blind Randomized Withdrawal periods

All of the above study changes will be captured as protocol deviations. Additionally, Jazz has developed a process to capture this data within comment fields in the EDC and has communicated guidelines across the sites in order to include this summary when the data are submitted to the FDA.

As subjects participating in the PK sub-study are required to be admitted in the investigative unit overnight, no alternative measures are feasible when sites are shut down or re-purposed as a COVID-19 public health emergency facility.

5.3. Study Treatment

During the OTTP, all subjects will receive open-label JZP-258 and are titrated to a tolerable and efficacious dose based on the recommendations summarized in Table 1.

Table 1: JZP-258 Dosing Recommendations

Dosing Regimen	Starting Nightly Dose	Titration Increments	Maximum Nightly Dose ^b
Once Nightly	≤3 g	≤1.5 g/night per week	6g
Twice Nightly	≤4.5 g (divided)	≤1.5 g/night per week	9g
Thrice Nightly (titration only, not a starting dose)	Not applicable	≤1.5 g/night per week	9g

Note: the aim of JZP-258 dose titration and optimization is to maximize efficacy (reduced IH symptoms, e.g. EDS, sleep inertia, and sleep duration) while ensuring adequate nocturnal sleep and minimizing risks associated with safety and tolerability

^aThe weekly increase in dose of ≤1.5 g/night may be made incrementally every few days as tolerated

^bThe maximum single dose should not exceed 6 g and the maximum nightly dose should not exceed 9 g at twice or thrice nightly dosing

EDS=excessive daytime sleepiness; IH=idiopathic hypersomnia

During the SDP, all subjects will receive open-label JZP-258 at the same unchanged dose that they received at the end of the OTTP.

During the DBRW, all subjects will receive blinded study drug. At the end of the SDP, subjects will enter the DBRW and will be randomized 1:1 to receive either JZP-258 (at the dose taken at the end of the SDP) or Placebo (at a volume and regimen equivalent to the JZP-258 dose taken at the end of the SDP).

During the OLE all subjects will receive open-label JZP-258. During the PK study, all enrolled subjects will receive open-label JZP-258 with no change in dose required.

Study drug will be dispensed at clinic visits and, if applicable, at intervals specified by state or local regulations or to resolve logistical issues.

5.4. Power and Sample Size Considerations

A sample size of 56 subjects randomized per treatment group (total randomized sample size of 112 subjects) will provide 91.8% power to detect a difference of 3.5 points for the change in ESS between JZP-258 and placebo, from the end of the SDP to the end of the DBRW. This study was originally designed to include an optional IA for efficacy; thus, calculations were based on the following: a 2-sample Z test with a group-sequential design including one IA at 60% information fraction using a Lan-Demets alpha spending function that approximates the O'Brien-Fleming boundaries, a common standard deviation (SD) of 5.5 points in the change in ESS for both arms, and a 2-sided significance level of 0.05. Assuming a 20% dropout rate prior to randomization, approximately 140 subjects will be enrolled.

5.5. Randomization and Blinding

An Interactive Web Recognition System (IWRS) vendor will prepare and retain the master randomization code for the entire study. The IWRS vendor will not be involved in the analysis of this study.

At the end of the SDP, subjects meeting randomization criteria will be randomized via IWRS 1:1 to either JZP-258 at the stable dose established in the previous 2 weeks or to Placebo at a volume equivalent to the JZP-258 dose that was established in the previous 2 weeks. Randomization will be stratified by the subject's use of stimulant agent and / or Xyrem at baseline per the following baseline medication group:

Group 1: subjects on Xyrem only

Group 2: subjects on Xyrem and an additional stimulant or alerting agent

Group 3: subjects not currently taking Xyrem but are taking a stimulant or alerting agent

Group 4: subjects not currently taking Xyrem or a stimulant or alerting agent.

A double-blind approach will be used during the DBRW. JZP-258 and JZP-258 placebo oral solution will be matched in volume, to ensure adequate blinding of the subject and study personnel. The Jazz study team, with the exception of the Jazz clinical trial material supply group will remain blinded until the formal database snapshot for the final comparative efficacy analysis.

During the DBRW a subject's treatment assignment should only be unblinded when knowledge of the treatment is necessary for immediate medical management of the subject. In the case of an immediate medical emergency, an Investigator or his / her designee will be able to unblind a subject at any time via the IWRS without any obligation to contact the Medical Monitor prior to emergency unblinding. The Investigator or his/her designee is responsible for all decisions

related to medical treatment in the study. A comment must be entered in the source documentation to specify the reason for unblinding, along with the date on which the code was broken and the identity of the person authorizing the unblinding. Subjects for whom the blind is broken will be withdrawn from the study. The Medical Monitor should be notified of the unblinding as soon as possible, but the results of the unblinding should not be disclosed to the Medical Monitor.

5.6. Timing of analyses

The final comparative efficacy analysis for this study will occur after all randomized subjects complete or discontinues the DBRW period. For these analyses, a formal database snapshot including data per a cut-off date is planned, which will occur after the last randomized subject completes or discontinues the DBRW period. Unblinding will occur after the data extraction is completed. This analysis will include results on the final comparative analyses of efficacy end points and all available safety, open-label efficacy, and pharmacokinetic data. These results will be summarized in an interim CSR.

A final analysis will occur after all subjects complete or discontinue from the study. These analyses will be based on a locked database and will include final summaries across the study on safety, open-label efficacy, and pharmacokinetic results. Results will be summarized in a final CSR.

5.7. Interim Analysis

5.7.1. Data Monitoring Committee

A data monitoring committee is not planned for this study.

5.7.2. Interim Analysis Method

This study was originally designed to include an optional IA for efficacy. However, the Jazz study team decided not to perform the interim analysis due to it not being operationally feasible, as full study recruitment has been achieved faster than originally anticipated.

6. ANALYSIS SETS

For the purpose of analysis, the following populations are defined:

Table 2: Analysis Sets

Analysis Set	Description
All Screened	
The all screened analysis set (SCR) will contain all subjects who provided a signed informed consent for this study.
 
This analysis set will be used to summarize the number of screened, screen failure and enrolled subjects.

Analysis Set	Description
Enrolled	
The Enrolled Analysis Set (ENR) will contain all subjects who provided a signed informed consent form (ICF) for this study and were deemed as meeting the inclusion/exclusion criteria of this study by the Investigator and were dispensed study drug.
 
This analysis set will be used to summarize subject disposition, major protocol deviations as classified in the Clinical Trial Management System (CTMS) [the study CRO, IQVIA, manages the CTMS], and inclusion/exclusion from each analysis set.

Safety	
The overall Safety Analysis Set (SAF) will include all subjects who took at least one dose of study medication. The SAF will also be defined for each study period:
 
 • The OTTP SAF will contain all subjects in the ENR who took at least one dose of open label (OL) study drug during the OTTP. Hence, the OTTP SAF will be the same as the overall SAF. • The SDP SAF will contain all subjects in the ENR who took at least one dose of OL study drug during the SDP. • The DBRW SAF will contain all subjects in the ENR who took at least one DB study drug. • The OLE SAF will contain all subjects in the ENR who took at least one dose of OL study drug during the OLE. 
The overall SAF will be used to summarize subjects' demographic and other baseline characteristics data, past medical conditions/diseases, surgical history, medications, IH diagnosis history data as well as exposure to study drug and all safety data; select outputs will also be provided for the DBRW SAF.

Randomized	
The Randomized Analysis set (RND) includes all randomized subjects. Subject disposition for the DBRW will be summarized using this analysis set.

Modified Intent-to-Treat	
The mITT Analysis Set (mITT) will include all subjects who are randomized to JZP-258 or Placebo, who received at least 1 dose of study drug during the DBRW and have at least one set of post randomization assessments for ESS or IHSS, or a PGIc value at end of DBRW.
 
A set of post randomization assessments is defined as having an end of SDP and end of DBRW value for ESS or IHSS. The mITT includes subjects with any primary or key secondary endpoint data.
 
This analysis set will be used for analyzing efficacy endpoints (primary,

Analysis Set	Description
	secondary, and exploratory). Demographics and other baseline characteristics data, past medical conditions/diseases, surgical history, and IH Diagnosis IH diagnosis history data will also be summarized using this analysis set. For summaries and analyses based on the mITT, subjects will be classified according to randomized treatment group.
PK	The PK Analysis Set will consist of all subjects who received JZP-258 and have any evaluable PK data from at least 1 post dose sample. This analysis set will be used for summarizing the Pharmacokinetic data. Demographic and other baseline characteristics data, as well as exposure to study drug will be summarized.

7. GENERAL ASPECTS FOR STATISTICAL ANALYSIS

The statistical principles applied in the design and planned analyses of this study are consistent with International Conference on Harmonization (ICH) E9 guidelines (ICH 1998).

7.1. General Methods

Analyses and summary outputs will be generated using SAS® version 9.4 (or higher). Categorical variables will be presented using counts and percentages. Unless otherwise specified, continuous data will be summarized using descriptive statistics comprising of the number of subjects with data to be summarized (n), mean, SD, median, minimum (Min) and maximum (Max).

For quantitative measurements, change from baseline will be calculated as:

- Change from baseline = Test value at visit X – baseline value

Unless otherwise specified, analyses based on mITT or DBRW SAF that intends to compare the two randomized treatment groups or to summarize the data during DBRW will be presented by randomized treatment group. In general, other analyses will be summarized by baseline medication groups. Summaries by baseline medication group (as defined in the electronic database) and baseline medication subgroup of efficacy analyses will be combined if there are too few subjects in any group.

- Group 1 and Group 2 will be combined if there are less than 10 subjects in either group and outputs will be summarized by Group 1 or 2 vs Group 3 vs Group 4.
- If the combined total of Group 1 and Group 2 is less than 10, then Groups 1, 2, and 3 will be combined. In this case, outputs will be summarized by Group 1 or 2 or 3 (Receiving Baseline IH Medication) vs Group 4 (Treatment Naïve).

7.2. Baseline and Study Day Definitions

7.2.1. Baseline

For all safety assessments and efficacy summaries across the study, baseline will be defined as the last non-missing measurement collected/ assessed prior to or on the same day of the first dose of study drug.

For efficacy summaries during the DBRW, baseline will be defined as follows:

- **ESS, IHSS, FOSQ-10, and WPAI:SHP:** for these assessments, the End of SDP measurement taken prior to or on the date of randomization will be used as baseline
- **TST and VAS:** for these assessments, baseline will be defined as the average from days with non-missing data within the last week of the SDP.

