7.2.2. Study Day

Two different types of study days will be calculated for this study:

- Study Day will be calculated based on the date of the first dose of open label (OL) study drug in the OTTP and will be used to show start and stop days of assessments and events during the study. Study Day 1 will be the day of the first dose of OL study drug in the OTTP.
- Period Day will be calculated based on the date of the start of the study period during which the assessments or events will be performed or occur to show start and stop days of assessments or events during the study period.

Study Days will be calculated as follows:

- Study Day= (date of assessment or event – date of first dose of OL study drug in the OTTP) if the date of assessment or event is before the date of first dose of OL study drug during the OTTP
- Study Day= (date of assessment or event – date of first dose of OL study drug in the OTTP) + 1 if the date of assessment or event is on or after the date of first dose of OL study drug during the OTTP

Period Days of each study period, after screening, will be calculated as follows:

Efficacy Data:

- OTTP Day= (date of assessment or event – Baseline Visit) + 1
- SDP Day= (date of assessment or event – End Titration Visit) + 1
- DBRW Day= (date of assessment or event – date of randomization) + 1
- OLE Day= (date of assessment or event –End of Double-blind Randomized Withdrawal Visit) + 1

Safety Data:

- OTTP Day= (date of assessment or event – start date of first dose of OL study drug in the OTTP) + 1
- SDP Day= (date of assessment or event – date of the first dose of OL study drug in the SDP) + 1
- DBRW Day= (date of assessment or event – date of the first dose of DB study drug in the DBRW) + 1
- OLE Day= (date of assessment or event – date of the first dose of OL study drug in the OLE) + 1

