10. SAFETY

Safety analyses will be based on the SAF and summarized across all study periods by Baseline Medication Group. In addition, data from the DBRW will be summarized by treatment group using the DBRW SAF. No inferential statistical analysis will be performed; only descriptive summaries will be provided.

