10.4. Vital Signs

The following vital signs measurements will be reported for this study.

- Sitting systolic blood pressure (SBP), (millimeter of mercury [mmHg])
- Sitting diastolic blood pressure (DBP) (mmHg)
- Sitting heart rate (beats per minutes [bpm])
- Sitting respiratory rate (breaths/min)
- Body Temperature (°C)
- Weight (kg)
- Height (cm)
- BMI (kg/m²) [derived]
- Pulse Oximetry (%) Screening and PK Nights only)

These vital signs (with the exception of the BMI which will be calculated programmatically) will be measured during the screening visit and each in-clinic scheduled visit. Height (cm) will be obtained at screening visit only.

The following summaries will be provided for vital signs data across all study periods

- Observed and change from baseline by visit
- Incidence of markedly abnormal criteria by visit

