10.4.1. Vital Signs Markedly Abnormal Criteria

Markedly abnormal quantitative vital signs measurements will be identified in accordance with the following predefined markedly abnormal criteria as specified in Table 5.

Table 5: Vital Signs Predefined Markedly Abnormal Criteria

Variable (unit)	Low	High
SBP (mmHg)	≤ 90 mmHg AND change from baseline ≤ -20 mmHg	≥ 180 mmHg AND change from baseline ≥ 20 mmHg
DBP (mmHg)	≤ 50 mmHg AND change from baseline ≤ -15 mmHg	≥ 105 mmHg AND change from baseline ≥ 15 mmHg
Heart rate (bpm)	≤ 50 bpm AND change from baseline ≤ -15 bpm	≥ 120 bpm AND change from baseline ≥ 15 bpm
Weight (kg)	percentage change from baseline $\leq -10.0\%$	percentage change from baseline $\geq 10.0\%$

Variable (unit)	Low	High
Temperature (°C)	≤ 35.0 °C	≥ 39.0 °C

Note: bpm: Beats per minute. DBP: Diastolic Blood Pressure. kg: kilogram. mmHg: Millimeter of mercury. SBP: Systolic Blood Pressure

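### Safety data have only a pre-titration baseline, so by-arm vital-sign and weight change in the randomized withdrawal period can show run-in JZP-258 effects under placebo

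*SAP*

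**What the plan says.** SAP 7.2.1 gives one rule for safety: "For all safety assessments and efficacy summaries across the study, baseline will be defined as the last non-missing measurement", on or before the day of the first dose of study drug. SAP 7.2.2 places that dose at the start of titration: "Study Day 1 will be the day of the first dose of OL study drug in the OTTP". A second rule in 7.2.1 opens "For efficacy summaries during the DBRW, baseline will be defined as follows" and moves the reference to the end of the SDP. It covers ESS, IHSS, FOSQ-10, WPAI:SHP, TST and the sleep-inertia VAS. No such rule exists for safety.

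SAP 7.1 defines "Change from baseline = Test value at visit X – baseline value" and says that summaries of DBRW data are generally presented by randomized group. SAP 10 adds: "In addition, data from the DBRW will be summarized by treatment group using the DBRW SAF". SAP 10.4 lists weight among the vital signs and plans "Observed and change from baseline by visit", plus the incidence of markedly abnormal values by visit. In Table 5 (SAP 10.4.1) the weight criterion is only a "percentage change from baseline" of at least 10% in either direction. Blood pressure and heart rate need both an absolute limit and a change. Temperature uses an absolute limit alone.

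Protocol 7.3.1 and 7.4.2 collect weight and vital signs at the End of Stable Dose and End of DBRW visits.

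**The concern.** The DBRW is the only placebo-controlled period, and safety is a secondary objective. A reader of a by-arm DBRW table will take the change under placebo as what happened on placebo. Under SAP 7.2.1 that change starts before titration and runs through the whole open-label exposure. A subject who lost 10% of body weight on JZP-258 and did not regain it in two weeks on placebo would be counted in the placebo column.

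Elsewhere the SAP keeps the periods apart. Safety data have their own DBRW day count (7.2.2), adverse events are assigned to the period of onset and tabulated by arm for the DBRW (10.2), and one exposure measure excludes placebo time (10.1.1). Change in vital signs and weight has no matching rule.

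**Working it through.** **1. Period lengths (Protocol 3.1, SAP 5.1).** Titration 10 to 14 weeks, SDP 2, DBRW 2, open-label extension 24. Their sum is (10 to 14) + 2 + 2 + 24 = 38 to 42 weeks, which reproduces the maximum treatment duration in Protocol 3.4.

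**2. Interval covered by change at End of DBRW.**
- On JZP-258 before randomization: 10 + 2 = 12 to 14 + 2 = 16 weeks.
- From safety baseline to End of DBRW: 12 + 2 = 14 to 16 + 2 = 18 weeks.
- Share before randomization: 12/14 = 85.7% to 16/18 = 88.9%.
- With the visit windows of Protocol Appendix 1.1 (End Titration day 63 to 98, SDP 14 to 17 days, DBRW 14 to 17 days), pre-randomization time is 63 + 14 = 77 to 98 + 17 = 115 days. The share runs from 77/(77 + 17) = 82% to 115/(115 + 14) = 89%.

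**3. Effect on the columns.** Let D be the mean change by End of SDP and r the fraction that reverses in two weeks on placebo. Assume that the JZP-258 arm stays at D.

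| | Pre-treatment baseline | End of SDP baseline |
|---|---|---|
| JZP-258 | D | 0 |
| Placebo | (1 − r)D | −rD |
| JZP-258 minus placebo | rD | rD |

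The difference between arms is the same under either baseline; only the columns differ. For r = 0, 0.5 and 1 the placebo column is D, 0.5D and 0 from the pre-treatment baseline, and 0, −0.5D and −D from End of SDP. The documents give neither D nor r.

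**4. Weight flag, illustration only.** The documents contain no weight-change data. Assume that percentage change by End of SDP is normal and that nothing is regained on placebo. Take 56 placebo subjects, the planned arm size.
- Mean −2, SD 3: P(change ≤ −10) = Φ(−8/3) = 0.004; × 56 = 0.2 subjects.
- Mean −3, SD 4: Φ(−7/4) = 0.040; × 56 = 2.2 subjects.
- Mean −4, SD 5: Φ(−6/5) = 0.115; × 56 = 6.4 subjects.

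With an assumed two-week SD of 1.5%, a 10% loss arising within the DBRW lies 10/1.5 = 6.7 SDs out, a probability near 0. On these assumptions, nearly every weight flag in the placebo column would date from the run-in.

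**The case against.** Several stronger readings are tempting, and the documents do not support them.

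- *The randomized comparison is biased.* It is not. Randomization follows the run-in, both arms carry it, and step 3 gives the same expected difference under either baseline. No inference is planned on safety data.
- *The placebo column mostly shows drug effect.* The 86% to 89% is elapsed time. Carry-over is the larger part of the open-label change only if less than half of it reverses in two weeks, and no reversal rate is given. Subjects on Xyrem at entry were already taking oxybate at the safety baseline, so their change is not new oxybate exposure.
- *Every threshold count is wrong.* A run-in fall in blood pressure or heart rate is flagged at End of DBRW only if both the absolute limit and the change are still met at that visit. Temperature is unaffected. Only weight is purely change-based.
- *The baseline should be replaced.* A change from End of SDP alone would make the ±10% weight flag almost unreachable in either arm and would hide a sustained loss on JZP-258. The pre-treatment value answers a legitimate question.

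Two further points stand. Observed values and across-study tables are planned, so the open-label shift is visible elsewhere. The by-arm vital-sign table is also implied rather than listed: SAP 6 promises only selected outputs for the DBRW safety set, and SAP 10.4 refers to all study periods. Adverse events, tabulated by period and arm, are unaffected.

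None of this supplies a by-arm change that starts at randomization. If the phrase about summaries across the study in 7.2.1 is read as limiting the safety rule too, DBRW safety has no stated baseline, and the same addition is needed.

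**Conclusion.** The gap is real and narrow. As written, any by-arm DBRW summary of vital-sign or weight change covers 14 to 18 weeks, of which 12 to 16 precede randomization. The change within the placebo arm and the ±10% weight flag can therefore attribute run-in JZP-258 effects to placebo. Blood-pressure and heart-rate flags are exposed only where the absolute limit still holds at End of DBRW.

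The interval arithmetic is firm. The effect size is not known: 0.2 to 6.4 of 56 subjects rests wholly on assumed weight distributions with no regain. Efficacy, type I error and the expected between-arm safety difference are untouched. This is an improvement worth making because it costs almost nothing; it is not a flaw that threatens the trial's conclusions.

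**What to change.** In SAP 7.2.1 and 10.4:

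- For by-arm DBRW summaries of vital signs and weight, add change from the End of SDP measurement alongside change from the pre-treatment baseline.
- For the change-based criteria in Table 5, keep the existing count and report separately the subjects who newly meet the criterion during the DBRW, that is, who did not already meet it at End of SDP.
- Keep the pre-treatment baseline for the across-study tables.
- State how subjects with a remote End of SDP visit are handled, since SAP Appendix 5 treats weight and vital signs as missed at remote visits.
- If no by-arm vital-sign change table is intended, say so.

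The cost is a few sentences, one extra baseline flag and an added column or row in the DBRW tables. No new data are needed.
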